17.6. Safety Analyses

The following variables are safety endpoints.

- AEs: Mapped to preferred term using the Medical Dictionary for Regulatory Activities (MedDRA)
- Injection site reactions/local tolerability in selected quadrant (through subject and Investigator reporting)
- Vital signs
- Laboratory testing

AEs will be summarized by treatment group. AE duration will be summarized using descriptive statistics by treatment group.

Descriptive statistics will be presented for each clinical laboratory test for the actual and change from screening at each visit by treatment group and vital signs for the actual and change from Day 1 pre-injection for each injection day at each visit by treatment group.

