^e Before injection.

^f Up to 4 hours before injection; approximately 15 and 30 minutes after injection. Vital signs must be stable before the subject is discharged.

^g Assessment made via photograph (if treatment session, use photograph taken before marking dimples).

^h All 4 quadrants are assessed at the Screening B visit; at other visits, the selected quadrant only is assessed.

ⁱ Initial Hexsel CSS at screening must be ≤ 13 on selected quadrant ([Appendix C](#)).

^j To qualify for treatment, the selected quadrant must have a score of 3 or 4 (moderate or severe) in both the CR-PCSS and PR-PCSS, and a Hexsel CSS score ≤ 13 ; to qualify a quadrant that had been previously treated with EN3835 in study EN3835-201, the quadrant must have CR-PCSS and PR-PCSS scores equal to or greater than study EN3835-201 baseline scores and a Hexsel CSS score ≤ 13 .

^k Medical history and prior medications will be based on EN3835-201 eCRF; only updates and concomitant medications need to be captured at Screening B visit.

^l Do not conduct if Screening B visit date is within 12 months of obtaining an ECG during the double-blind study (EN3835-201).

^m Do not conduct on subjects eligible and opting-in for a second course of treatment in the current study (EN3835-202) if Screening B visit or Day 1 visit for second treatment course is the same day as Day 71 of the first treatment course in this study or previous study EN3835-201.

ECG=Electrocardiogram; eCRF=Electronic case report form; EFP=Edematous fibrosclerotic panniculopathy; Tx=Treatment

NOTE: Subject cellulite assessments must be completed before the Investigator cellulite assessments are conducted at each visit.

Table 4: Assessments for Durability (Beyond Day 360)

Procedures	Long-term Durability Visit 1 Day 450 ^a (±30 days)	Long-term Durability Visit 2 Day 540 ^a (±30 days)	Long-term Durability Visit 3 Day 630 ^a (±30 days)	End of Long-term Durability Study Day 720 ^a or EOS/ET (±30 days)
Informed Consent	X			
Inclusion/Exclusion	X			
Digital photography	X	X	X	X
Medical history/EFP history including previous treatments	X ^b			
Prior/Concomitant Medications/Procedures	X ^b	X	X	X
Subject cellulite assessments:				
• Patient Reported Photonumeric Cellulite Severity Scale (PR-PCSS)	X ^{c,d}	X ^{c,d}	X ^{c,d}	X ^{c,d}
Investigator cellulite assessments:				
• Clinician Reported Photonumeric Cellulite Severity Scale (CR-PCSS)	X ^d	X ^d	X ^d	X ^d
• Hexsel Cellulite Severity Scale (CSS)	X ^d	X ^d	X ^d	X ^d

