NOTE: EN3835 is a foreign protein and Investigators must be prepared to address and manage an allergic reaction should it occur. At the time of each injection, a 1:1,000 solution of epinephrine for injection, 50-mg diphenhydramine injection or a suitable equivalent, and oxygen should be available and the Investigator and site staff must be familiar with their use.

Care Procedures After Injection

To evaluate the subject for possible immediate immunological AEs, the subject will remain in direct observation of medical personnel who are skilled in the management of an allergic reaction for 30 minutes after receiving the injection of study drug and until the subject exhibits no sign of an immunological or other clinically significant systemic or local AE. The subject's vital signs should be stable before the subject can leave direct observation (see section 14.8).

The Investigator or qualified designee will then apply a sterile dressing to the injection site with hypoallergenic tape. The subject will be instructed to remove the dressing in the evening.

12.1.4.3. Treatment Session 2 (Treatment Visit 2/Day 22 ± 3 Days) and Treatment Session 3 (Treatment Visit 3/Day 43 ± 3 Days)

Pre-injection

1. Record concomitant medications/procedures (section 12.2)
2. Body weight measurements
3. Vital sign measurements (section 14.8)
4. Collection of samples for urine pregnancy testing (section 14.7)
5. Digital photograph of selected quadrant before dimple marking (section 13.1)

6. Subject assessment of the severity of cellulite using photograph of the selected quadrant via PR-PCSS (section 13.1.1.1). NOTE: Complete the subject (PR-PCSS) assessment before the Investigator (CR-PCSS) assessment and before dimple marking.
7. Investigator will conduct an independent live assessment of the severity of cellulite using the CR-PCSS (section 13.1.1.4). The investigator will conduct the assessment of severity only after the subject has completed her rating of her quadrant and without knowledge of the subject's rating of her quadrant.
8. Selection and marking of dimples to be treated (section 12.1.4)
9. Digital photograph after dimple marking (section 13.1)

Injection

Administration of study drug in the prone position (section 12.1.4.2)

Post-injection

1. Record number of dimples treated and number of injections administered
2. Vital sign measurements (section 14.8)
3. Injection site reactions and local tolerability
4. AEs (section 14)

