17.6.5. Vital Signs

Descriptive statistics for vital signs (eg, systolic and diastolic blood pressure, pulse rate, respiratory rate, temperature, and body weight) and their changes from baseline at each visit and at the end of treatment visit will be presented.

Vital sign values are potentially clinically significant (PCS) if they meet both the observed value criteria and the change from baseline criteria. The criteria for PCS vital sign values will be detailed in the Statistical Analysis Plan (SAP). A listing of all AEs for subjects with PCS vital signs will also be provided.

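### Post-injection vital signs at sessions 2 and 3 appear to be compared with Day 1 instead of the same session's pre-injection reading, and the safety baseline is not stated for every cohort

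*Combined protocol and SAP*

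**What the plan says.** Section 17.6 (Protocol Amendment 4) sets the references for change. For vital signs it gives "vital signs for the actual and change from Day 1 pre-injection for each injection day at each visit by treatment group". For laboratory tests: "Descriptive statistics will be presented for each clinical laboratory test for the actual and change from screening at each visit by treatment group". It does not say which screening is meant.

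Section 17.6.5 uses a different term. Vital signs "and their changes from baseline at each visit and at the end of treatment visit will be presented", with no definition of baseline. It adds: "Vital sign values are potentially clinically significant (PCS) if they meet both the observed value criteria and the change from baseline criteria". The numerical criteria are left to a separate SAP, and no such text is in the documents supplied.

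Table 3, footnote f, fixes the measurement times at every treatment session: "Up to 4 hours before injection; approximately 15 and 30 minutes after injection". Table 12 shows the same scheme, with temperature taken before injection and at 30 minutes only.

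For subjects who are only observed, section 17.2.1 plans safety analyses on the Observational population. Table 2 marks no vital signs or laboratory sample at Screening A. It has vital signs at Days 90, 180, 270 and 360 and a laboratory sample at Day 360 only, with days counted from Day 1 of EN3835-201.

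**The concern.** The 15- and 30-minute readings exist to show what happens straight after an injection. The natural comparison is the reading taken just before it, on the same day. A Day 1 reference at sessions 2 and 3 adds day-to-day variation to the change. It can hide a fall when the Day 1 value happened to be low, and produce an apparent fall when it was high. Later sessions matter here because section 12.1.4.2 describes the product as a foreign protein and asks for observation for immediate immunological events.

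The PCS rule requires a change criterion as well as an observed-value criterion. If the same Day 1 reference is used there, the flag is affected as well as a column of means.

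A secondary gap is that the primary objective in section 9.1 covers enrolled subjects who choose no treatment, but no reference for their vital-sign or laboratory change is named.

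**Working it through.** **Readings affected.** The plan gives no figure of its own to reproduce; the counts come from Tables 3 and 12.

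- Sessions fall on Days 1, 22 (±3) and 43 (±3). A Day 1 reference is therefore 22 − 1 = 21 days old (18 to 24) at session 2 and 43 − 1 = 42 days old (39 to 45) at session 3.
- Blood pressure, pulse and respiratory rate: 3 sessions × 2 post-injection times = 6 readings per course. Of these, 2 × 2 = 4 (67%) have a reference from another day.
- Temperature: 3 × 1 = 3 post-injection readings, of which 2 have a reference from another day.
- With each session's own reference, 6 of 6 and 3 of 3 are same-day changes.

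**Possible effect on the PCS flag.** The documents give no vital-sign SDs and no PCS limits, so everything in this part is assumed for illustration. For systolic pressure: between-subject SD 10 mmHg, day-to-day within-subject SD *s* = 5 to 12, reading-to-reading SD 5, mean 115 to 125, change criterion a fall of at least 20, observed-value criterion 90 or below.

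SD of change:
- Same session: √(2 × 5²) = 7.1.
- Against Day 1: √(2 × (5² + s²)) = 10.0 at *s* = 5 and 18.4 at *s* = 12.

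Change criterion alone:
- No drug effect: P(change ≤ −20) = Φ(−20/7.1) = 0.2% same session; Φ(−20/10.0) = 2.3% to Φ(−20/18.4) = 13.8% against Day 1.
- True 30 mmHg fall: Φ(10/7.1) = 92.1% same session; Φ(10/10.0) = 84.1% to Φ(10/18.4) = 70.7% against Day 1.

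Section 17.6.5 requires both criteria, so the relevant quantity is the joint probability. With mean μ and true fall δ, the post-injection reading is N(μ − δ, 10² + s² + 5²). The change is N(−δ, 2 × 5²) with covariance 5² (same session), or N(−δ, 2 × (5² + s²)) with covariance 5² + s² (Day 1). The bivariate normal probability that the reading is ≤ 90 and the change is ≤ −20, for δ = 30, is below (losses from unrounded values):

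| Mean | s | Same session | Day 1 | Loss (points) |
|---|---|---|---|---|
| 115 | 5 | 62.3% | 59.3% | 3.0 |
| 115 | 12 | 58.4% | 51.9% | 6.5 |
| 120 | 5 | 47.7% | 46.0% | 1.7 |
| 120 | 12 | 47.3% | 43.3% | 4.0 |
| 125 | 5 | 32.9% | 32.0% | 0.8 |
| 125 | 12 | 36.2% | 34.1% | 2.1 |

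With no drug effect (δ = 0), false flags against Day 1 run from about 0.05% (mean 125, *s* = 5) to 3.2% (mean 115, *s* = 12). Against the same-session value they are at most 0.04%.

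**Observation-only subjects.** For a subject who never attended Screening B, 0 of 4 vital-sign visits and 0 of 1 laboratory visits in Table 2 have a Day 1 or screening reference within EN3835-202. A subject whose quadrants all failed at Screening B stays under observation and does have Screening B vital signs and, where scheduled, laboratory values (section 12.1.4.1). For one cellulite endpoint, section 17.5.1 names the EN3835-201 baseline as the reference; nothing similar is written for vital signs or laboratory tests.

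**Second course.** Subjects who had placebo in EN3835-201 may have two courses here (section 12.1.4), each with its own Day 1, and section 17.6 does not say which applies. Table 3, footnote m, also drops the Screening B laboratory sample when the second course's Screening B or Day 1 visit coincides with Day 71 of the first, and no substitute is named.

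**The case against.** The strongest reply is that the wording is ambiguous, not wrong. The phrase about each injection day can be read as that day's own pre-injection value, and section 17.6.5 says only baseline. This stands: the text needs clarifying and is not a certain error. It does not remove the point, because two programmers could build different tables from the same sentence.

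A reader might infer that acute reactions would go unnoticed. The documents do not support that. Subjects are observed directly for 30 minutes by staff able to manage an allergic reaction (section 12.1.4.2). The investigator reviews all vital-sign values, those judged clinically significant are recorded as adverse events, and signs must be stable before the subject leaves (section 14.8). Actual values are summarised as well.

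A reader might also take 92% against 71% as the loss in detection. Those figures use the change criterion alone, while the rule needs both criteria. Nor is it established that the PCS change criterion uses Day 1, since its baseline is undefined and its limits are deferred to a SAP that may settle the matter.

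Finally, a single fixed baseline is a legitimate choice for showing change across visits. That stands, and it is a reason to keep it for that purpose.

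**Conclusion.** On its plain reading, section 17.6 compares two thirds of the post-injection readings in each course with a value three or six weeks old when a better reference is already collected. No section clearly specifies a same-session change. This affects the descriptive change tables and possibly the PCS flag. Under the assumed limits and SDs, with both criteria applied, the loss in flagging a true 30 mmHg fall is about 1 to 6.5 points. These figures show direction and order of size; they are not estimates for this trial.

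It would go too far to say that observation-only subjects have no Day 1 or screening value, or that their safety results cannot be produced. They have a Day 1 in EN3835-201, some have Screening B values, and actual values and adverse events can be reported for all of them. What is missing is a stated reference for change, which is a secondary point of definition.

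**What to change.** In sections 17.6 and 17.6.5:

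1. Summarise the 15- and 30-minute readings as change from that session's own pre-injection value, and use the same reference for the PCS change criterion at those readings.
2. For between-visit display in treated subjects, keep change from the pre-injection value on Day 1 of the relevant treatment course.
3. State the vital-sign and laboratory baseline for observation-only subjects: the EN3835-201 values from before the first injection if they are available, otherwise actual values only.
4. Name the laboratory reference for a second course when footnote m omits the Screening B sample, for example the sample taken that day at the Day 71 visit.

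Items 1, 2 and 4 cost wording and programming and need no new measurement. Item 3 depends on EN3835-201 vital-sign and laboratory data being available to merge. The subject number carries over (section 12.1.3), but these documents do not show that the data exist.

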17.6.1. Prior, Concomitant, and Follow-up Medication

The World Health Organization (WHO) Drug Dictionary will be used to classify prior and concomitant medications by therapeutic class. The version used in this study will be stated in the Data Management Plan. Prior medication will be defined as any medication with a start date prior to the Day 1 date. Concomitant medication is defined as any medication with a start date on or after the Day 1 date or reported as ongoing. Any medications started after the last dose of study drug will be considered as follow-up medications.

Prior and concomitant medication use will be summarized descriptively by the number and percentage of subjects receiving each medication within each therapeutic class. Multiple use of the same medication by a subject will be counted only once.

17.6.2. Study Drug Exposure

For those subjects that elect, are eligible, and do receive treatment, the number of injections will be summarized by counts and percentages. The number of dimples treated will be summarized with counts and percentages.

17.6.3. Measurement of Treatment Compliance

All doses are administered while the subjects are at the investigational site. Any dose that was not administered per protocol will recorded as a protocol deviation by the Investigator.

17.6.4. Adverse Events

The MedDRA dictionary will be used to code AEs. The version used in this study will be stated in the Data Management Plan.

Descriptive statistics (the number and percentage) for subjects reporting TEAEs will be tabulated by system organ class and preferred term; by system organ class, preferred term, and severity; and by system organ class, preferred term, and relationship to study drug. If more than 1 AE is coded to the same preferred term for the same subject, the subject will be counted only once for that preferred term using the most severe and most related occurrence for the summarization by severity and by relationship to the study drug.

SAEs and AEs leading to premature discontinuation of study drug will be summarized. Listings will be presented for subjects with SAEs, subjects with AEs leading to discontinuation, and subjects who die (if any).

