Adverse events			Monitored Throughout Study	

^a Days listed reflect time from Day 1 visit in the double-blind study (EN3835-201).

^b Only updates to medical history, prior medications, and concomitant medications need to be captured at this visit.

^c Assessment made via photograph.

^d Only the quadrant treated with active EN3835 in study EN3835-201 is assessed for subjects participating in durability assessments beyond Day 360.

EFP=Edematous fibrosclerotic panniculopathy; EOS=End of study; ET=Early termination

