9. OBJECTIVES

9.1. Primary Objective

The primary objective of this study is to assess long-term safety of EN3835 0.84 mg at scheduled intervals over 1 year (12 months) or more in all subjects with EFP who elect to enroll in this open-label trial regardless of their decision to receive treatment (re-treatment or re-dosing) of open-label EN3835 or opt to receive no treatment.

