11.3.1. Subject Inclusion Criteria for Observation

1. Voluntarily sign and date an informed consent agreement
2. Participated in and completed the double-blind study EN3835-201
3. Received active EN3835 in the double-blind study EN3835-201
4. Achieved an improvement of at least 1 level on both the CR-PCSS and the PR-PCSS at the same visit on or before Day 71 in the double-blind study EN3835-201
5. Be willing to apply sunscreen to the EN3835-201 treated quadrant before each exposure to the sun while participating in the study (ie, screening through end of study)

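### Only selected EN3835-201 responders have adverse-event monitoring scheduled beyond Day 360, yet section 17.6.4 reports crude percentages with no onset interval or person-time, so early and late events cannot be separated

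*Combined protocol and SAP*

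**What the plan says.** All references are to Protocol Amendment 4.

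- **Objective (9.1).** To assess "long-term safety of EN3835 0.84 mg at scheduled intervals over 1 year (12 months) or more in all subjects with EFP".
- **Schedule (section 5).** Treated women are seen on Days 1, 22, 43 and 71 (Table 3), then at Days 90, 180, 270 and 360 (Table 2). Table 4 adds Days 450, 540 and 630 and a last visit headed "End of Long-term Durability Study Day 720", which may instead be an end-of-study or early-termination visit. Table 4 days count from Day 1 of EN3835-201. In Tables 2 and 4 the adverse-event row reads "Monitored Throughout Study". Table 4 has no rows for vital signs, laboratory tests or local tolerability.
- **Who enters Table 4 (11.3.1, 11.3.2).** Women who consent, received active drug in EN3835-201 and "Achieved an improvement of at least 1 level on both the CR-PCSS and the PR-PCSS at the same visit on or before Day 71". Retreatment of that quadrant excludes a woman, as does other cellulite treatment. Footnote d adds: "Only the quadrant treated with active EN3835 in study EN3835-201 is assessed for subjects participating in durability assessments beyond Day 360".
- **Analysis.** Safety is analysed within four cohorts (17.2). Women untreated in EN3835-202 form a separate Observational population (17.2.1). Section 17.6 says "AEs will be summarized by treatment group". Section 17.6.4 says "Descriptive statistics (the number and percentage) for subjects reporting TEAEs will be tabulated by system organ class and preferred term", with further splits by severity and relationship and one count per woman per preferred term. Exposure is described by injections and dimples only (17.6.2). The list of abbreviations gives a TEAE a start but no end.
- **Collection window (14.5.1, 14.5.2).** AEs and SAEs are collected from consent to 30 days after the last dose. SAEs judged related are reportable at any time.

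**The concern.** The percentage of women with at least one event rises with the time they are watched. If some women are followed to about Day 360 and others to Day 720, two groups with the same true rate will show different percentages, and a pooled percentage refers to no defined period. Follow-up beyond Day 360 is also not a random subset, because it depends on response in EN3835-201.

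The single count per preferred term adds to this. Section 8.3.1.2 describes local injection-site events that resolved within 3 weeks. A woman with early bruising who later has a new event under the same term adds nothing to the table. In a study whose primary objective is long-term safety, late onset is the information wanted, and the planned AE tables have no place for it.

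**Working it through.** **1. The plan's own figure.** There is none to reproduce. Section 17.1 gives about 350 subjects with no event rate or precision target. The event rates below are therefore assumptions.

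**2. Scheduled visits.** Days 1, 22, 43, 71, 90, 180, and so on to 720 give gaps of 21, 21, 28 and 19 days, then 90 days each.

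**3. Follow-up by group, reading Tables 2 and 4 as written.**
- Observational population: to about Day 360 for most women and up to Day 720 for Table 4 responders, counted from EN3835-201 Day 1. Entry to EN3835-202 follows Day 71, so the time actually watched in this study is about 360 − 71 = 289 days against at most 720 − 71 = 649 days.
- Safety population: a single-course woman has 360 days from her first EN3835-202 injection. A re-dosed Table 4 responder who starts on EN3835-201 Day D (assumed) has max(D + 360, 720) − D days.

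**4. Crude percentage at one common rate.** P = 1 − exp(−r × t/365.25), where r is the assumed constant first-event rate.

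| Rate per 100 person-years | 360 days | 540 days | 720 days |
|---|---|---|---|
| 5 | 4.8% | 7.1% | 9.4% |
| 10 | 9.4% | 13.7% | 17.9% |
| 20 | 17.9% | 25.6% | 32.6% |

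For the 289- and 649-day windows at 10 per 100 person-years: 1 − exp(−0.1 × 289/365.25) = 7.6% and 1 − exp(−0.1 × 649/365.25) = 16.3%.

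Re-dosed responders against 360 days (9.4%) for a single course, at 10 per 100 person-years:

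| Start D | Days followed | Ratio to 360 | Crude % |
|---|---|---|---|
| 90 | 630 | 1.75 | 15.8% |
| 180 | 540 | 1.50 | 13.7% |
| 270 | 450 | 1.25 | 11.6% |
| 360 or later | 360 | 1.00 | 9.4% |

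**5. Front-loaded events.** Assume 80% of women are affected by Day 73 and the later rate is 5 per 100 person-years. Then P = 1 − 0.2 × exp(−0.05 × (t − 73)/365.25), which gives 80.8% at 360 days and 81.7% at 720. The distortion is small here, but so is the visibility of late events.

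**6. Person-time.** Expected first events per woman are 1 − exp(−rt), with t in years. Expected person-years at risk are (1 − exp(−rt))/r. The ratio is r whatever the follow-up, so 5, 10 and 20 per 100 person-years are recovered at both 360 and 720 days.

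**7. The collection window.** Under 14.5.1, a three-session course ends AE collection at about Day 43 + 30 = Day 73. That is 73/360 = 20% of the way to Day 360 and 73/720 = 10% of the way to Day 720. This cannot be squared with the AE rows of Tables 2 and 4.

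**The case against.** - **No cohort comparison is planned.** Safety is tabulated within cohort, untreated women are reported separately, and no between-cohort test is proposed. This stands, and the point is descriptive. But unequal follow-up also sits inside one column, the Observational population, and readers will compare adjacent columns.
- **The largest contrast is a ceiling.** A reader might infer a 2.2-fold difference in observation time between cohorts (649/289). The documents do not support that. It contrasts responders with other untreated women, whom the plan never sets side by side. Table 4 also allows an earlier last visit. The estimated dates in the synopsis (Oct-2016 to Jun-2018) allow at most about 637 days in EN3835-202.
- **The direction between treated cohorts is not fixed.** Former placebo subjects may take a second course after Day 71, giving at least about 70 + 360 = 430 days from first injection, or 1 − exp(−0.1 × 430/365.25) = 11.1% in step 4. This stands.
- **Fewer contacts.** Section 14.2 asks at each visit about events since the last one, so elapsed time is covered. Sparser visits alone do not establish under-reporting.
- **Section 14.5.1 may govern.** Unequal follow-up would then largely disappear for non-serious AEs in single-course women, but collection would fall well short of the 12 months in the objective. Either reading leaves a problem.
- **A SAP might add such tables.** The protocol mentions a SAP, deferring criteria for clinically significant vital signs and laboratory values to it. The combined document contains no separate SAP text, so this cannot be checked.

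**Conclusion.** The point holds as a limitation of the planned AE tables, and it should be fixed. As written, they pool unequal and selectively extended follow-up, cannot separate early from late events, and give no rate per unit of follow-up. At one assumed rate of 10 per 100 person-years, follow-up length alone moves the crude percentage from 9.4% (360 days) to 13.7% (540 days, a re-dosed responder starting at Day 180) or 17.9% (720 days). These figures assume a constant rate, full attendance and the Table 2 and 4 reading of AE monitoring. The distortion matters mainly for late or infrequent events.

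A reader might go further and infer that the study cannot show long-term safety at all. The documents do not support that. Twelve months of follow-up is scheduled for each treated quadrant, with vital signs at the 3-month visits and laboratory tests and antibodies at Day 360. SAEs, deaths and discontinuations are listed individually.

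Separately, sections 14.5.1 and 14.5.2 contradict the AE rows of Tables 2 and 4. This must be reconciled before any late-event table can be interpreted.

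**What to change.** 1. Reconcile sections 14.5.1 and 14.5.2 with Tables 2 and 4, so that one AE and SAE collection window is stated.
2. In 17.6.4, keep the overall tables and add TEAEs and SAEs by onset interval: Days 1–71, 72–180, 181–360 and beyond 360. For each interval give subjects under observation, person-years and first-event incidence per 100 person-years. Count a woman afresh in each interval. Report follow-up time by cohort.
3. Use one clock per woman. For treated women it is the first EN3835 injection in EN3835-202. If there are two courses, assign each AE to the most recent one, so that injection-site events of a second course are not read as late events of the first. For observation-only women it is EN3835-201 Day 1, with person-time counted from entry to EN3835-202. Show never-treated women separately.
4. Limit side-by-side cohort percentages to onset by Day 360 of that clock.
5. Show events in the Day 450–720 follow-up separately, with Table 4 participants as denominator, and describe them as a selected responder subset. For re-dosed women this display can overlap with item 2, so the two must not be added.

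The analysis changes need protocol or SAP wording and one extra set of tables from dates already collected. The cost is more output and small denominators in the late intervals.
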